5.2. Statistical and Analytical Plans

5.2.1. General Considerations

All data will be entered, verified, and archived at a contract research organization (CRO) external to Lilly and/or at Lilly. Data listings, summaries, and analyses will be performed by a CRO and/or by Lilly under the guidance and approval of statisticians at Lilly. Statistical analysis of this study will be the responsibility of Lilly.

Any change to the data analysis methods described in the protocol will require an amendment ONLY if it changes a principal feature of the protocol. Any other change to the data analysis methods described in the protocol, and the justification for making the change, will be described in the statistical analysis plan and/or in the clinical study report (CSR). Additional exploratory analyses will be conducted, as deemed appropriate.

The patient populations used in the study are described below:

1. All Patients Entered: all patients who entered this study and completed Visit 1.
2. All Randomized: all patients who were randomized to a treatment arm.
3. Full Analysis Set (FAS): based on the intent to treat (ITT) principle, all patients who were randomized and who have taken at least one dose of study medication. Patients are assigned to the treatment arm to which they were randomized.
4. Per-protocol (PP): patients in the FAS/ITT population who also meet the following criteria:
 - a. violate no inclusion or exclusion criteria
 - b. have not discontinued from the study prior to 24 weeks
 - c. have not been off study medication for more than 10 consecutive days during the treatment period
 - d. have not received chronic (lasting longer than 14 consecutive days) systemic glucocorticoid therapy (excluding topical, intra-articular, intraocular, and inhaled preparations)

Unless otherwise specified, listings will be prepared using all randomized patients. Efficacy and safety analyses will be conducted using the FAS population. Selected analyses will be conducted using the All Randomized population and the PP population.

Unless otherwise noted, all tests of treatment effects will be conducted at a 2-sided alpha level of 0.05, and confidence intervals (CIs) will be calculated as 2-sided 95% CIs. All tests of interactions between treatment groups and other factors will be conducted at a 2-sided alpha level of 0.05. No adjustments for multiplicity will be performed. See Section 5.2.7 for the gate-keeping strategies used for primary/secondary endpoints.

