Pseudo-hypoglycemia: an event during which the person with diabetes reports any of the typical symptoms of hypoglycemia with a measured plasma glucose concentration >70 mg/dL (> 3.9 mmol/L) but approaching that level.

Besides the hypoglycemic categories listed above, total hypoglycemic event will be defined as follows:

Total hypoglycemic event: any event which is either documented symptomatic hypoglycemia, asymptomatic hypoglycemia, probable symptomatic hypoglycemia or severe hypoglycemia.

For each category of hypoglycemia event, the incidence, the number of hypoglycemic events per patient, the rate of hypoglycemic events per year (that is, the number of hypoglycemic episodes per patient per patient year [365.25 days]) will be calculated. These measures will be summarized at baseline, titration, maintenance, and overall study periods and at endpoint.

The proportion of patients with at least 1 hypoglycemic event (total, severe, nocturnal, and others) or incidence during the study will be summarized (counts and percentages) and analyzed using Fisher's exact test or the Pearson's chi-square test for the FAS population.

Logistic regression will be used as a sensitivity analysis of the incidence of hypoglycemia. The model will have presence or absence of hypoglycemia as the dependent or response variable and treatment, baseline HbA_{1c}, pre-study treatment (Lantus®-bolus, other basal-bolus, premixed insulin), and pre-study metformin or acarbose usage (metformin only, acarbose only, or neither) as the independent terms in the model.

The rate of hypoglycemic episodes per year (total, severe, nocturnal, and others) will be analyzed at baseline, titration, maintenance, and overall study periods and at endpoint using the Wilcoxon test. In addition, the hypoglycemia rates will also be analyzed using a negative binomial model for the FAS population with terms for treatment, baseline HbA_{1c}, pre-study treatment (Lantus®-bolus, other basal-bolus, premixed insulin), and pre-study metformin or acarbose usage (metformin only, acarbose only, or neither).

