1. The relationship between the natural logarithm of the last observed insulin antibody levels (Ln[antibody level]) and selected clinical response variables (efficacy and safety measures (eg HbA_{1c}, total hypoglycemia rate, basal dose [U/day, U/kg/day], total dose [U/day, U/kg/day], premeal dose [U/day, U/kg/day]) will be evaluated using scatterplots and analyzed using ANCOVA on efficacy/safety measure as the dependent variable with treatment, pre-study treatment (Lantus®-bolus, other basal-bolus, premixed insulin), and pre-study metformin or acarbose usage (metformin only, acarbose only, or neither) as fixed effects; baseline HbA_{1c} level, Ln(antibody level) and treatment-by-Ln(antibody level) interaction as covariates for the FAS patients with detectable antibodies postbaseline and with valid antibody testing at baseline (detected, ND). A significant treatment-by-insulin antibody interaction may be indicative of a differential treatment effect necessitating further exploration to determine the nature of the interaction. Only patients with non-missing baseline value and at least one non-missing post-baseline value of the clinical response variable will be included in the analysis.
2. The relationship between TEAR and selected clinical response variables (efficacy and safety measures (e.g. HbA_{1c}, total hypoglycemia rate, basal dose [U/day, U/kg/day], total dose [U/day, U/kg/day], premeal dose [U/day, U/kg/day]) will be analyzed using ANCOVA on efficacy/safety measure as the dependent variable with treatment, TEAR (yes/no), pre-study treatment (Lantus®-bolus, other basal-bolus, premixed insulin), and pre-study metformin or acarbose usage (metformin only, acarbose only, or neither) , treatment-by-TEAR interaction as fixed effects and baseline HbA_{1c} level as a covariate for the FAS patients with detectable antibodies postbaseline and with valid antibody testing at baseline (detected, ND). A significant treatment-by-TEAR interaction may be indicative of a differential treatment effect necessitating further exploration to determine the nature of the interaction. Only patients with non-missing

baseline value and at least one non-missing post-baseline value of the clinical response variable will be included in the analysis.

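### The antibody section tests total hypoglycemia rate by ordinary ANCOVA; if TEAR is related to the rate and the TEAR groups differ in size, the 5% interaction test can be well off its level.

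*SAP*

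**What the plan says.** SAP 5.2.11.4 evaluates whether antibody level and TEAR affect clinical response. Items 1 and 2 put several responses through one model form. After HbA1c, the list reads "total hypoglycemia rate, basal dose [U/day, U/kg/day], total dose [U/day, U/kg/day], premeal dose [U/day, U/kg/day"]. In item 2 each response "will be analyzed using ANCOVA on efficacy/safety measure as the dependent variable with treatment, TEAR (yes/no"), prestudy treatment, prestudy metformin or acarbose use, the treatment-by-TEAR interaction and baseline HbA1c. Item 1 replaces TEAR by the natural log of the last antibody level. Both are run "for the FAS patients with detectable antibodies postbaseline and with valid antibody testing at baseline (detected, ND").

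The interaction is read as a flag: "A significant treatment-by-TEAR interaction may be indicative of a differential treatment effect necessitating further exploration to determine the nature of the interaction". SAP 5.2.1 sets the level: "All tests of interactions between treatment groups and other factors will be conducted at a 2-sided alpha level of 0.05".

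Elsewhere the same outcome is treated as a count. SAP 5.2.11.2 uses the Wilcoxon test and adds that "the hypoglycemia rates will also be analyzed using a negative binomial model for the FAS population". Protocol 12.2.9.3 gives that model a log treatment-duration offset. SAP 5.2.12 tests the subgroup-by-treatment interaction on the hypoglycemia rate with a negative binomial model and the log of exposure in days as offset. SAP 5.2.11.4 gives no reason for doing otherwise.

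**The concern.** Two things follow from the text alone. A treatment interaction on the hypoglycemia rate is tested on the ratio scale for subgroups and on the difference scale for TEAR. And the antibody section uses a constant-variance model for an overdispersed count divided by follow-up time, whose variance rises with its mean.

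The second matters for the interaction test. ANCOVA estimates one residual variance, dominated by the larger TEAR group, and applies it to all four treatment-by-TEAR cells. The standard error of the interaction depends mainly on the smaller TEAR group. If that group has the higher rate, its variance is understated and the test rejects too often; if it has the lower rate, the test rejects too seldom. So the error rate moves with the association that this part of the SAP sets out to examine. At stake is a false flag of a difference between the biosimilar and the reference, or a test far stricter than its stated 5%.

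**Working it through.** **1. The plan's own figure, used to set the number of patients.** From SAP 5.1.1: margin 0.40, SD 1.05, two-sided 0.05, 80% power. n = 2 × (1.960 + 0.842)² × 1.05² / 0.40² = 108.2, so 109 completers per arm (power 80.3%). 109 / 0.85 = 128.2, so 129 randomized per arm, 258 in total. This agrees with the plan. The antibody models use only patients with detectable postbaseline antibody, and the size of that subset is not given. I assume half of 258, that is 129 patients in both arms together; 30% and 80% were also tried with TEAR unrelated to the rate.

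**2. Other assumptions, none of them in the documents.** Mean rate 40 per patient-year (1 and 5 also tried), negative binomial dispersion k from 0.5 to 4, TEAR share p from 10% to 50%, TEAR-to-non-TEAR rate ratio r from 0.5 to 2. The 15% dropout is the plan's; uniform exposure among dropouts is assumed.

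**3. Large-sample approximation.** Over full follow-up (24/52 year) the variance of a patient's rate is about k × 40² + 40 / (24/52). With k = 1 this is 1600 + 87, so variance is nearly proportional to the mean squared and the TEAR-to-non-TEAR variance ratio is about r². With balanced arms and the same TEAR share in each, the true variance of the interaction estimate divided by the variance that ANCOVA uses is

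V = [r²(1 − p) + p] / [p r² + (1 − p)],

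and the actual level is 2 × [1 − Φ(1.96 / √V)].

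- p = 0.3, r = 2: V = 3.1 / 1.9 = 1.63; 1.96 / 1.277 = 1.53; level 12.5%.
- p = 0.1, r = 2: V = 3.7 / 1.3 = 2.85; 1.96 / 1.687 = 1.16; level 24.5%.
- p = 0.3, r = 0.5: V = 0.475 / 0.775 = 0.61; 1.96 / 0.783 = 2.50; level 1.2%.
- p = 0.5 or r = 1: V = 1; level 5%.

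**4. Simulation with the SAP's ANCOVA terms.** No treatment effect, no interaction, 129 patients, k = 1 to 2, about 5,000 trials per setting (Monte Carlo error about 0.6 points at 5%).

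| TEAR rate ratio | 10% TEAR | 30% TEAR | 50% TEAR |
|---|---|---|---|
| 0.5 | 0.3% to 0.5% | 1.2% to 1.4% | 4.6% to 5.1% |
| 1.5 | 13.8% to 14.1% | 8.4% to 8.9% | 5.2% to 5.3% |
| 2 | 21.3% to 23.0% | 11.9% to 12.1% | 4.9% to 5.6% |

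This agrees closely with step 3 at 30% and 50% TEAR and shows the same pattern at 10%. A simpler simulation without covariates (120 patients, 20% TEAR, mean 15 events per 24 weeks, gamma shape 1) gave 17%, 12%, 5.5% and 0.6% at rate ratios 2, 1.5, 1 and 0.5.

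**5. Skew alone.** With TEAR unrelated to the rate, ANCOVA rejected in 4.5% to 5.9% of trials for k from 0.5 to 2, over all subset sizes and TEAR shares tried, and in 4.1% to 6.7% at k = 4.

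**6. Item 1 (continuous log antibody level).** Rejection was 5.3%, 6.9%, 13.2% and 7.3% at rate ratios per log unit of 1.0, 1.2, 1.5 and 0.8.

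**7. Alternatives.** Negative binomial with log-exposure offset (Wald test, k = 1, 600 trials per setting, error about 2 points): 5.3% to 7.2% at 30% TEAR and 7.8% to 8.1% at 10% TEAR. The SAP's ANCOVA with HC3 standard errors, in the settings of step 4: 3.0% to 5.3%.

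**The case against.** The strongest reply is that this is a screening flag. A significant result only prompts further exploration, and nothing is decided on it. The section also provides box plots, scatterplots, listings and adverse-event comparisons by TEAR status. Items 1 and 2 name eight responses each, so about 16 interaction tests, with no multiplicity adjustment; exact 5% control for one of them was never a property of the set. All of that stands, and it limits the weight of the point. It does not explain why one outcome gets two different interaction models.

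The size also rests on assumed inputs. TEAR requires detectable antibody and the models keep only patients with detectable postbaseline antibody, so the TEAR share there is at least that among all tested patients; as it nears 50%, the problem disappears. That stands too.

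The negative binomial is not exact either, was checked on data generated from its own model, and changes the question from differences to ratios. When treatment and TEAR effects both multiply, ANCOVA rejected in 9.5% to 16.9% of trials at 30% TEAR, and part of that is a real interaction on the difference scale. This is why the scale must be stated and why robust ANCOVA is a fair alternative.

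A reader might infer that non-normal errors by themselves break the test. Step 5 shows that they do not. A reader might also infer that the test has been shown to hide real differences. Every setting had no interaction on at least one scale and power was not measured; all that is shown is a level well below 5% in some settings.

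**Conclusion.** The inconsistency is certain and needs no assumption: SAP 5.2.11.4 fits constant-variance ANCOVA to an outcome that 5.2.11.2 and 5.2.12 model as negative binomial. The loss of the 5% level is conditional. It requires that TEAR (or antibody level) is related to the hypoglycemia rate and, for item 2, that the TEAR groups are unequal in size. With about 120 to 129 patients and 10% to 30% TEAR, the level is then about 8% to 23% if the smaller TEAR group has 1.5 to 2 times the rate, and about 0.3% to 2% if it has half the rate. Otherwise it is near 5%. The documents give neither the TEAR share nor the relation, so no single actual level can be stated, and they do not support saying without condition that the test fails. It would also be wrong to carry the point over to the primary noninferiority test or the main hypoglycemia comparison; both use other models and are unaffected. This is a worthwhile correction to an exploratory analysis.

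**What to change.** For total hypoglycemia rate only, in items 1 and 2 of SAP 5.2.11.4, choose one of the following and say on which scale the interaction is measured:

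- Fit the negative binomial model to the event count with the terms already listed, including the interaction, and log exposure as offset, as in SAP 5.2.12. The interaction is then a ratio of rate ratios. This matches the rest of the SAP. Its drawback is that the test is slightly liberal in small TEAR cells, at about 6% to 8%.
- Keep the difference scale and the ANCOVA, but test the interaction with heteroscedasticity-consistent (HC3) standard errors. This tends to be somewhat conservative.

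The one not chosen can serve as a sensitivity analysis. Keep ANCOVA for HbA1c and the insulin doses. Report the number of patients and events in each treatment-by-TEAR cell, so that readers can judge how far to trust the test.

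The cost is a few lines of SAP text and a change of procedure for one outcome. No new data are needed. Protocol 12.2.9.1 says only that the antibody relationship will be looked into and names no model, so the change contradicts nothing in the protocol.

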5.2.11. Safety Analyses

5.2.11.1. Adverse Events

Adverse events will be listed by patient, system organ class, Medical Dictionary for Regulatory Activities® (MedDRA) preferred term, severity, and relationship to the study disease, drug, device, or procedure for all patients. Adverse events will be summarized as treatment-emergent adverse events (TEAEs) for the FAS population. Treatment-emergent adverse events are defined as events that are newly reported after first study treatment following randomization, or reported to worsen in severity from baseline. The proportion of patients experiencing each TEAE will be presented by preferred term, system organ class (SOC), and treatment group. The proportion of patients experiencing each TEAE that are assessed as possibly related to the study disease, drug, device, or procedures will also be summarized. The number and proportion of patients will be presented and compared by treatment using Fisher's exact test or Pearson's chi-square test for the FAS population. TEAEs will be summarized by preferred term within SOC and by preferred term by decreasing frequency.

All SAEs will be listed by patient and summarized by treatment as counts and percentages. If a sufficient number of SAEs are reported, the proportion of patients with SAEs between treatment groups will be compared using Fisher's exact test. Similar analyses will be performed for discontinuations due to AEs.

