The level of total insulin antibodies (expressed as percent binding) will be summarized by descriptive statistics (mean, median, SD, Q1, inter-quartile range (IQR), Q3, standard error, minimum, and maximum) at baseline, each visit, and endpoint (LOCF). At each of these time points, the median level of percent binding will be compared between treatment groups using the Wilcoxon rank sum test. Graphical displays of median percent binding and IQR at each visit and endpoint (LOCF) by treatment will be presented. These analyses will be performed for the FAS population, for patients with antibody levels detectable at baseline and without detectable levels at baseline.

All of the analyses above will be performed for the level of cross-reactive antibodies as well.

Categorical shift tables for total insulin antibodies with 4 categories (nondetectable, [0.26, 1.26), [1.26, 5), ≥ 5.0) of the level of insulin antibodies from baseline to endpoint (LOCF) and from baseline to maximum postbaseline value will also be presented.

Categorical shift tables for cross-reactive antibodies with 4 categories (nondetectable, [1.06, 2.06), [2.06, 5), ≥ 5.0) of the level of cross-reactive antibodies from baseline to endpoint (LOCF) and from baseline to maximum postbaseline value will also be presented.

The number and proportion of patients who have a treatment-emergent antibody response (TEAR) will be summarized by treatment at each post-baseline visit, at the 24-week endpoint (LOCF), and overall for the 24-week treatment period, then analyzed using Fisher's exact test or Pearson's chi-square test. Treatment-emergent AR is defined as an absolute increase of at least 1% in insulin antibody levels (measured in % binding) AND at least 30% relative increase from baseline [for patients who are insulin antibody-positive at baseline], or turning from insulin antibody-negative status at baseline to insulin antibody-positive during the course of the study with at least 1.26% binding (1% above the lower limit of detection) following treatment with study drug. The TEAR definition for patients who were antibody-negative at baseline takes into account the assay variability near the cut point of the assay (detectable antibody if $\geq 0.26\%$).

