For patients with TEAR, a visit-wise listing of total and cross-reactive insulin antibody percent binding and clinical outcomes (HbA_{1c}, total hypoglycemia rate, basal insulin dose (U/Day, U/kg/Day), TEAE preferred terms) will be presented. The listing will be sorted by treatment and endpoint total insulin percent binding.

Incidence tables showing the number and percent of patients with initial and continuing TEAR at each visit will be presented. Similar analyses will be performed for the detection of total insulin antibodies and for the detection of cross reactive insulin antibodies.

Box plots of clinical outcomes (HbA_{1c}, total hypoglycemia rate, basal dose) will be generated by treatment and TEAR status.

In addition, the following patient listings of insulin antibodies (percent binding) will be provided for patients with TEAR: a listing of level of total insulin antibody percent binding across visit sorted by treatment and maximum postbaseline percent binding; a listing of level of total insulin antibody percent binding across visit sorted by treatment and endpoint percent binding. Similar listings will be presented for cross reactive percent binding.

In addition, the potential impact of total insulin antibody level and TEAR status on clinical response will be evaluated in several ways:

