3. The relationship between TEAR and overall incidence of categories of adverse events (TEAE, SAE, TEAE related to study drug, special topic allergic reactions, injection site reactions) will be assessed by showing the proportion of patients with an event for TEAR and non-TEAR patients by treatments for the FAS. For patients with and without TEAR, treatments will be compared using the Mantel-Haenszel test and the odds ratio and p-value from this test will be reported. The homogeneity of the odds ratios for TEAR and non-TEAR patients will be assessed using the Breslow-Day test.

The potential impact of cross-reactive antibody formation on clinical response similar to the analyses above will be done if there is sufficient number of patients with cross-reactive antibodies.

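### SAP 5.2.11.4 item 3 names no TEAR window and does not require an adverse event to follow the antibody response, so a true association would be diluted in the displayed proportions

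*SAP*

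**What the plan says.** SAP 5.2.11.4 states a purpose: "the potential impact of total insulin antibody level and TEAR status on clinical response will be evaluated". Item 3 is one of three ways of doing so. It takes up "The relationship between TEAR and overall incidence of categories of adverse events" (TEAEs, SAEs, drug-related TEAEs, allergic events, injection-site reactions), and the display is "showing the proportion of patients with an event for TEAR and non-TEAR patients by treatments for the FAS".

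Three other places fix the timing:

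- **TEAR.** For a patient negative at baseline, TEAR means "turning from insulin antibody-negative status at baseline to insulin antibody-positive during the course of the study with at least 1.26% binding". For a patient positive at baseline it is a rise in binding of set size, also with no time limit within the study. TEAR is summarised "at each post-baseline visit, at the 24-week endpoint (LOCF), and overall for the 24-week treatment period". Item 3 does not say which of these it uses.
- **Events.** SAP 5.2.11.1 defines TEAEs as "events that are newly reported after first study treatment following randomization, or reported to worsen in severity from baseline". Under Protocol 10.3.1.1, SAE collection starts once the patient has consented and received investigational product.
- **Samples.** Protocol 7.2.2.4 and Attachment 1 place the post-baseline antibody samples at Visits 4, 8, 11 and 13 (Weeks 2, 6, 12 and 24) or early discontinuation.

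Neither document limits item 3 to events after TEAR, sets a landmark visit, or lets TEAR status change over time.

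**The concern.** The clinical question is whether an antibody response leads to more allergic, injection-site or other events. That needs the response to come first. In item 3 the patient carries one label for the whole period, while events are counted from first dose. Events from the time before the response are thus placed in the TEAR column. If TEAR raises the later event rate, the TEAR column mixes time at the raised rate with time at the ordinary rate, and the contrast with non-TEAR patients shrinks.

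At stake is how far a reassuring table can be trusted. Anti-glargine antibodies and injection-site reactions are both named in a secondary safety objective (SAP 4.2), so the table is likely to be read as evidence on that question.

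**Working it through.** The documents give no figure for this analysis: no TEAR rate, TEAR timing or event rate. All sizes below rest on stated assumptions.

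**1. The windows side by side.** Take a patient with a rash in Week 1 whose antibody samples are negative at Weeks 2, 6 and 12 and first meet TEAR at Week 24. Under the 24-week endpoint window the patient is TEAR, and under the overall window likewise. The rash is a TEAE because it follows first dose. The patient therefore counts as a TEAR patient with an event under either window.

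**2. Share of treatment time before the response.** Assume first positives fall equally on Weeks 2, 6, 12 and 24. True onset lies between the preceding sample and the first positive one, so the two ends are:

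- onset at the first positive sample: (2 + 6 + 12 + 24)/4 = 11 weeks; 11/24 = 0.458, or 46%
- onset at the preceding sample: (0 + 2 + 6 + 12)/4 = 5 weeks; 5/24 = 0.208, or 21%

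**3. Apparent rate ratio.** With a constant underlying rate and share *s* of time before the response, apparent ratio = *s* + RR × (1 − *s*).

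| True RR | *s* = 0.208 | *s* = 0.458 |
|---|---|---|
| 2 | 0.208 + 2 × 0.792 = 1.79 | 0.458 + 2 × 0.542 = 1.54 |
| 3 | 0.208 + 3 × 0.792 = 2.58 | 0.458 + 3 × 0.542 = 2.08 |
| 5 | 0.208 + 5 × 0.792 = 4.17 | 0.458 + 5 × 0.542 = 3.17 |

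**4. The same on the scale item 3 shows.** Assume a 24-week risk of 5% without TEAR and a true doubling after onset. A patient with share *s* before onset has risk 1 − 0.95^(2 − *s*).

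- Onset at the first positive sample (*s* = 1/12, 1/4, 1/2, 1): 9.4%, 8.6%, 7.4%, 5.0%; mean 7.6%
- Onset at the preceding sample (*s* = 0, 1/12, 1/4, 1/2): 9.75%, 9.4%, 8.6%, 7.4%; mean 8.8%

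The table would show 7.6% to 8.8% against 5.0%, a ratio of 1.5 to 1.8. A doubling present from first dose would show 1 − 0.95² = 9.75% against 5.0%, a ratio of 1.95.

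**5. Simulation.** Assumptions: 20% of patients TEAR; 24-week event risk 5% or 40%; dropout 0 or 15%, not driven by adverse events; first positives spread early (50/25/15/10% over the four visits), evenly, or late (10/20/30/40%).

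- *No true effect:* the TEAR versus non-TEAR odds ratio is 1.00 with full follow-up and 1.03 to 1.09 with 15% dropout, because longer follow-up gives more chance of both TEAR and an event. Of the events counted in TEAR patients, 28% to 64% precede the first positive sample and 20% to 49% precede onset.
- *True doubling:* the odds ratio is 1.57 to 1.87 at 5% risk. A doubling from first dose would give (0.0975/0.9025)/(0.05/0.95) = 2.05. At 40% risk it is 1.78 to 2.28, against (0.64/0.36)/(0.40/0.60) = 2.67.
- *Counting events and person-time from true onset* returns 0.98 to 1.00 under no effect and 1.98 to 2.01 under a doubling. True onset is not observed in the trial, so a real analysis can only bracket it.

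**The case against.** **The p-values do not test TEAR against non-TEAR.** This stands. In item 3 "treatments will be compared using the Mantel-Haenszel test and the odds ratio and p-value from this test will be reported", within TEAR and non-TEAR patients, and Breslow-Day checks whether the two treatment odds ratios agree. A reader might infer that the tests themselves misattribute events to TEAR. The documents do not support that: the dilution sits in the side-by-side proportions. The same event counts feed the tests, but no error in the treatment comparisons has been shown.

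**The plan already gives timing.** In part. For TEAR patients there is a visit-wise listing that includes TEAE terms, and there are tables of initial and continuing TEAR by visit. The listing has no non-TEAR comparison and no counting rule, and the tables do not link events to onset.

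**Early withdrawal could reverse the association.** A reader might infer this, since a patient who leaves early because of an adverse event has fewer samples in which to show TEAR. No calculation supports a reversal. Simulated dropout moved a null odds ratio only to 1.03 to 1.09, upward, though it did not model withdrawal caused by events. Two features blunt the problem. A sample is taken at early discontinuation, and SAP 5.2.11.4 limits the antibody analyses to FAS patients with a valid baseline and at least one valid post-baseline test, although item 3 itself says only FAS.

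**The size may be overstated.** Quoting 46% alone would be. It is the upper end under an even spread, which is itself assumed.

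**A time-ordered analysis has its own misclassification.** This stands. Starting TEAR time at the first positive sample puts events between true onset and that sample into non-TEAR time, and the last sampling gap is 12 weeks. That is why it should supplement the planned table and not replace it.

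**Conclusion.** The point holds as an inexpensive improvement to a supportive safety analysis. Item 3 leaves the TEAR window unstated and sets no order between response and event, so its proportions understate a true association. Assuming an even spread of first positives and a constant underlying rate, a true rate ratio of 2 would appear as about 1.8 to 1.5, 3 as 2.6 to 2.1, and 5 as 4.2 to 3.2. The spread is not in the documents: earlier responses would mean less dilution, later ones more.

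A reader might also infer that the table would create a false association. With equal follow-up and no true effect it does not; unequal follow-up adds only a small upward shift in the simulated settings. The sample size and the HbA1c noninferiority conclusion do not depend on this analysis.

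**What to change.** In SAP 5.2.11.4 item 3:

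1. State which TEAR window defines TEAR and non-TEAR patients, and keep the planned table.
2. Add a summary of events per patient-year in TEAR and non-TEAR time, by treatment. Start TEAR time at the first TEAR-positive sample, and count earlier time and events as non-TEAR. Use FAS patients with a valid baseline and at least one valid post-baseline antibody test, and say that this restriction governs item 3. Say also how time is counted if TEAR does not continue at later visits.
3. Repeat the summary with TEAR time starting at the last preceding TEAR-negative sample (baseline for those first positive at Week 2). The two versions bracket the unknown onset.

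The cost is SAP wording and programming. Event and sample dates are collected, and the by-visit tables of initial TEAR already require the visit of first response. There are limits. Onset is known only to within a sampling interval of up to 12 weeks. Patients first TEAR-positive at Week 24 contribute no on-treatment TEAR time in the first version. Event counts will be small, so the results should be labelled supportive.
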